1.4 DIVERSITY AND INCLUSION

The study will involve 12 sites, including remote costal population and cities. The 12 sites will include centres in the Southwest, North England and Scotland. This will help with capturing a diverse national population along with patients from deprived areas. As this is a hospital study, all adult patients referred to the PERT team will be screened. The study will collect data from intermediate and high-risk patients who are affected by cancer and pregnant women who have an increased risk of clotting (11). Both populations were excluded from previous clinical trials, although the risk of radiation during pregnancy needs to be acknowledged.

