2.2 SECONDARY OBJECTIVES

- 1. To identify factors that determine the decision to use thrombectomy within the PERT team
- 2. To evaluate the factors that predict outcome of CAVT
- 3. To evaluate the patient tolerance and experience in the form of patient related outcome measures (PROMS) of CAVT

- 4. To evaluate the effectiveness and risk profile of CAVT in high-risk patients, including effects of concurrent lytic therapy where given
- 5. To evaluate the effect of service design on PE CAVT rate and outcomes
- 6. To compare variability in provision of CAVT between hospitals and its effect on performance and outcomes.
- 7. To evaluate the relationship between severity and outcome in patients receiving CAVT
- 8. To determine imaging features that are associated with poor outcomes in patients undergoing CAVT
- 9. To determine the effectiveness of CAVT in relationship to the age of the thrombus
- 10. To evaluate the perceived dyspnoea at 30 days and 6 months after CAVT, and also in comparison to the non-intervened group
- 11. To evaluate Quality of life as assessed by EQ-5D-5L and PEmb-QoL at 30, 90 days and 6 months for all participants.
- 12. Incidence of device related SAE(s)
- 13. Evaluate the impact of the length of procedure time and the operator decided end point of CAVT, including technical success and its effect on outcomes
- 14. To evaluate the time to CAVT and its effect on outcomes and resource utilisation.

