2.2 OUTCOMES

Effectiveness of CAVT will be determined by the change in RV/LV ratio on Echocardiography and the reduction in direct invasive measurement of the Pulmonary artery pressure at the beginning and end of the procedure.

Technical success will be determined by the operator comparing pre and post imaging and pulmonary artery pressures. Morbidity and mortality will be expressed as percentage of the cohort. Imaging features, service design, PERT team decision and comorbidities effect on outcomes will be assessed via regression analysis.

The service design and effect on thrombectomy will be assess by service questionnaire at site set up describing the service design factors. Patient reported outcomes like quality of life and breathlessness will be assessed to determine improvement as per their validated questionnaires.

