4.4 STUDY ASSESSMENTS

Data will then be collected regarding admission information, imaging parameters, decisions to treat and how the patient was treated. Data will be collected by the research nursing team and will be maintained on anonymised electronic research specific (Dendrite) database.

Follow up

Follow up data, including 30 days, 90 days and 6-month outcomes will be assessed. The follow up with the questionnaires will be administered by the Dendrite platform.

Organisation

A short service-based questionnaire will be sent to each centre to establish centre-specific systems such as on call rota, PERT team activation, reporting practices and capture data around routine decision-making at that site. This will be completed by the site team at registration at each site and will take approximately 5 minutes to complete.

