6.2 ANALYSIS

Patient demographic and clinical characteristics will be summarised using appropriate descriptive statistics. The primary outcome, change in LV/RV ratio before and at 48 hours post baseline will be summarised according to risk group and overall and will be assessed with a two-sided paired t-Test. Linear regression analysis will be used to identify factors, including severity, affecting the change in LV/RV ratio. Survival analysis will be used to model factors affecting mortality. Data will be analysed using R or Stata. An unblinded interim analysis at 100 patients will be performed at 6 month follow up with focus on the primary outcomes. No Stop/Go criteria will be applied as the PE response team decision to treat or not is not protocolised and the study is observational only. A detailed statistical analysis plan will be written with the University of Plymouth Medical Statistics group and finalised before database lock.

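### Service design is a hospital-level exposure with at most 12 values, but the protocol puts it in an unspecified regression with patient-level factors and names no hospital term

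*Protocol*

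**What the plan says.** Protocol 2.2 Secondary Objectives, item 5, reads: "To evaluate the effect of service design on PE CAVT rate and outcomes". Item 6 asks how CAVT provision varies from one hospital to another and what follows from that variation.

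The exposure is collected per centre. Under 2.2 Outcomes, service design and its effect on thrombectomy "will be assess by service questionnaire at site set up describing the service design factors". Section 4.4 adds: "A short service-based questionnaire will be sent to each centre to establish centre-specific systems such as on call rota, PERT team activation". The site team completes the form once, at registration. Section 1.4 gives the number of centres: "The study will involve 12 sites".

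On analysis, 2.2 Outcomes says: "Imaging features, service design, PERT team decision and comorbidities effect on outcomes will be assessed via regression analysis". Section 6.2 names two models: "Linear regression analysis will be used to identify factors, including severity, affecting the change in LV/RV ratio" and "Survival analysis will be used to model factors affecting mortality". Neither section mentions hospital as a cluster, random effects, robust standard errors or a site-level analysis. Section 6.2 leaves the detail to an SAP that is still to be written.

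**The concern.** All patients at a hospital share the same value of every service factor. The information about such a factor therefore comes from 12 hospitals, not from 200 or 2,000 patients. The sentence in 2.2 Outcomes lists service design beside imaging features, the PERT decision and comorbidities, which vary from patient to patient, and gives all of them one regression.

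Taken literally, a patient-level linear regression would test a two-level service factor on 198 or 1,998 residual degrees of freedom, when 12 hospitals in two groups supply 10. Its standard error is right only if hospitals do not otherwise differ, and objective 6 exists because they may.

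At stake is whether ordinary differences between hospitals are reported as effects of the on-call rota, PERT activation or reporting practice, in results that could shape how services are organised.

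**Working it through.** The protocol states no power or error figure for the service-design analyses, so there is none to reproduce.

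**Inputs from the protocol.** 12 hospitals (1.4); 2,000 participants and 200 thrombectomy patients (Study Summary). Patients per hospital: 2,000/12 = 166.7 and 200/12 = 16.7. The follow-up echocardiogram is scheduled only for CAVT patients (7.2, Appendix 1), so RV/LV change belongs to the 200. CAVT use, mortality and the questionnaires belong to the full cohort.

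**Assumptions.** No true service effect; a two-sided 5% test; hospital ignored in the model. The intraclass correlation (ICC) is not in the protocol. It is taken as 0.01 to 0.05, with values outside that range shown.

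**Formulas.** Design effect DE = 1 + (m − 1) × ICC, where m is patients per hospital. True error of the unadjusted test = 2 × [1 − Φ(1.96/√DE)].

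**Worked example, ICC 0.05.**
- 200 patients: DE = 1 + 15.7 × 0.05 = 1.78; 1.96/√1.78 = 1.47; error 14.2%.
- 2,000 patients: DE = 1 + 165.7 × 0.05 = 9.28; 1.96/√9.28 = 0.64; error 52.0%.

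| Assumed ICC | DE, n = 200 | True error | DE, n = 2,000 | True error |
|---|---|---|---|---|
| 0 | 1.00 | 5.0% | 1.00 | 5.0% |
| 0.005 | 1.08 | 5.9% | 1.83 | 14.7% |
| 0.01 | 1.16 | 6.8% | 2.66 | 22.9% |
| 0.02 | 1.31 | 8.7% | 4.31 | 34.5% |
| 0.05 | 1.78 | 14.2% | 9.28 | 52.0% |
| 0.10 | 2.57 | 22.1% | 17.57 | 64.0% |

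**Checks by simulation.**
- Continuous outcome, hospitals split 6/6 or 4/8, 20,000 runs: within about 1 point of the table. A separate set of 3,000 runs per setting (6/6) gave 7.0% and 14.4% for 200 patients, and 22.2% and 53.2% for 2,000, at ICC 0.01 and 0.05.
- CAVT rate of 10%, 12 × 166 patients, logistic Wald test, 5,000 runs: 22.4% at ICC 0.01 and 51.0% at 0.05.
- Unequal hospital sizes (coefficient of variation 0.5): somewhat worse. For 200 patients, 7–8% at ICC 0.01 and 16–18% at 0.05; for 2,000 patients, 26% and 54%.
- A t-test on the 12 hospital means (10 df) held 4–5% in every setting.

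**Several factors.** The number to be tested is not stated. If three independent factors were tested on CAVT rate (an assumption), the chance of at least one false positive would be 1 − (1 − 0.224)³ = 53% at ICC 0.01 and 1 − (1 − 0.510)³ = 88% at ICC 0.05.

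**What a valid analysis can detect.** With 12 hospitals split 6/6, a two-sided 5% t-test has 80% power only for a difference of about 1.8 standard deviations of the hospital means.

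**Limits.** Mortality by a Cox model was not simulated. Questionnaire outcomes will have fewer than 2,000 responses if some are not returned, which lowers m and the inflation.

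**The case against.** The strongest reply is that the protocol states no error. Regression analysis is a broad term that covers mixed models and a regression on 12 site values, and survival analysis covers shared frailty. Every remedy proposed here is thus already permitted, and choosing among them for secondary objectives is ordinary SAP work. The linear-regression sentence in 6.2 does not mention service design. No logistic model for CAVT rate appears anywhere, so the largest figures belong to an analysis that the protocol has not named. No ICC is given, and alpha 0.05 appears only with the sample-size statement.

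Much of this stands. A reader might infer that the protocol commits to ordinary patient-level regression with patients treated as independent. It does not say so. A reader might also infer that spurious service findings are very likely, or close to certain. That does not fit the 7–14% for RV/LV change, the one outcome that 6.2 assigns to linear regression. In the full cohort it would need hospital to be ignored, an ICC near 0.05 or above, and several factors tested.

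Two things remain. The protocol does name methods, and it places a hospital-level exposure in the same regression as patient-level factors; an SAP that followed this literally would carry the problem forward. And 12 units is a property of the design, which no SAP can change. Section 6.1 justifies 200 and 2,000 patients without saying that objectives 5 and 6 rest on 12 hospitals.

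**Conclusion.** The concern holds in conditional form. Service design has at most 12 independent values, and the protocol does not say how hospital enters the regression that is to assess it. If the named methods are run without accounting for hospital, a nominal 5% test has a true error of about 7–14% for RV/LV change in the 200 CAVT patients and about 22–53% for CAVT rate or another outcome analysed in all 2,000. The ranges take in both the formula and the simulations, and rest on an assumed ICC of 0.01–0.05.

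The primary paired comparison is not affected by this point. Because the objectives are secondary and the remedy is cheap, this is a change that should be made, not one that puts the study in doubt.

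**What to change.** In 2.2 Outcomes and 6.2, separate the service-design and between-hospital questions from the patient-level predictors, and state:

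- **Model.** A random intercept for hospital: a linear mixed model for RV/LV change, a mixed logistic model for CAVT use, and a shared-frailty Cox model for mortality. Alternatively, a regression on the 12 case-mix-adjusted site estimates.
- **Degrees of freedom.** Test hospital-level factors on about 10 df: Kenward-Roger or Satterthwaite for the linear model, and a comparable small-sample reference or the site-level regression for the others.
- **Scope.** Name a few service factors in advance, call these analyses exploratory, and say that they rest on 12 hospitals.
- **Patient-level predictor models.** Keep hospital in these too, so that patient factors are not confounded with site.

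If the SAP already specifies this, the protocol needs only a matching sentence. Section 4.5 allows for additional sites if recruitment is slow; it is worth noting there that, for objectives 5 and 6, the number of hospitals matters more than the number of patients.

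The cost is a few sentences and slightly more analysis work. No new data are needed, because presenting hospital and transfers in are already data items in 7.2. The downside is wider confidence intervals and few detectable service effects, which is what 12 hospitals can support.

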3 STUDY PARTICIPANTS

3.1 SCREENING PROCEDURES

All patients identified as having an CT confirmed PE and referred to the hospitals PERT team will be screened. Patients who attend hospital over a 2-year period with a CT diagnosed pulmonary embolism will be stratified, into low, intermediate or high risk as per normal standard of care using the PESI score. This is an internationally regarded score that enables PEs to be categorized according

to severity. All patients who are intermediate or high risk and referred to the local Pulmonary Embolism Response Team (PERT) and if eligible will be approach for consenting to enter the study.

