3.2 INCLUSION CRITERIA

Patient:

- 1. Clinical signs and symptoms consistent with acute PE with duration of 14 days or less
- 2. Patients who present with CT confirmed PE
- 3. Defined as intermediate or high-risk PE (as defined within the ESC Guidelines¹)
- 4. Date of CT imaging within the two-year study period.
- 5. Patient is ≥ 18 years of age
- 6. Informed consent obtained
- 7. Evidence of cardiac dysfunction (Either biochemical or imaging features of RHS)

Operator:

1. Operator experience treating a minimum of 2 previous PE's and experience with Penumbra indigo systems (defined as 3 cases).

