3.3 EXCLUSION CRITERIA

- 1. Known serious, uncontrolled sensitivity to radiographic agents
- 2. CT not available to evaluate PE
- 3. Low risk PE as defined by ESC guidelines¹
- 4. Current participation in another investigational drug or device study that may confound the results of this study. Studies requiring extended follow-up for products that were investigational but have since become commercially available are not considered investigational studies.
- 5. Other medical, social, or psychological conditions that, in the opinion of the Investigator, precludes the patient from appropriate consent, could limit the patient's ability to participate in the study.

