4.2 RECRUITMENT

Patients will be assessed for inclusion into the study by the research nursing team or trained member of the PERT team at point of referral to the local PERT team. Consent for inclusion in the data recording can be sought retrospectively in an out of hours setting, up to 96 hours post referral. All patients referred with an intermediate or high-risk PE (according to ESC guidelines (1)) will be included (after consent) into the wider dataset, with more specific data collected on those undergoing CAVT treatment.

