6 STATISTICS

6.1 THE NUMBER OF PARTICIPANTS

Target sample size is based on recruitment of 12 centres, based on estimates from current PE Response team referrals and previous year thrombectomy numbers. We estimate that each centre will see around 130 eligible patients per year and perform approximately 13 thrombectomies per year (4). Therefore, across the 12 centres we expect to see around 3000 eligible patients and around 300

thrombectomy patients across the two years. We expect around 70% of patients to consent to take part in the study due to its observational nature and therefore we expect between 2000 of PERT referred patients and 200 thrombectomy patients across the two years. These allow for approximately 30% of eligible patients to decline to participate in the study which is higher than the STRIKE PE (8) rate.

The interim analysis of the STRIKE PE (8) study demonstrated a change of LV/RV ratio of (mean reduction of 0.38 (SD \pm 0.27) (P< .001)) at 48 hours, which is equivalent to an effect size of d >1 (Cohen's d). However, the STRIKE PE study was within a European setting and with different thresholds for treatment than current UK based guidelines. We are therefore conservatively anticipating approximately 25% of the thrombectomy group being classified as high risk. Therefore, our patient group, we anticipate a smaller change in LV/RV ratio which is still clinically significant. With a sample size of 200 we would be able to detect a standardised effect size of d=0.2 (Cohen's d) at 90% power with an alpha 0.05. As a key comparison of interest of the high-risk subgroup at 90% power a small effect size will be detectable.

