7.1 DATA FLOW DIAGRAM

7.2 DESCRIPTION OF THE DATA

Sample data points will include the following for **ALL** patients:

Patient demographics

Age, Sex, Medical History, Cancer, Pregnancy, Time of first symptoms, presenting hospital, admission from location (e.g. Own Home/nursing home) transfer in, previous PE, Anticoagulation, Concurrent DVT and Position.

Admission / Diagnosis (at point of diagnosis of PE if not on admission)

Admission observations, Biochemistry including Temperature, BP, Pulse, oxygen saturations and GCS, biochemistry including: WCC, RBC, CRP, GFR and BNP and Troponin

CT findings (including Evidence of RHS parameters including IVC contrast reflux, Septal flattening, clot location, reporter grade)

Base line (Day of referral to PERT if not day of admission)

PESI score, , RV/LV ratio CT, RV/LV ratio USS. Presence of right atrial clot, PFO presence on Echocardiography, eligibility for thrombolysis (e.g. recent head trauma/ ischaemic stroke, previous ICH, Intracranial neoplasm, GI malignancy, GI haemorrhage in previous 21 days, Recent surgery, BP >185, active bleeding, infective endocarditis, Clotting abnormalities), If Thrombolysis given, including dose.

PER Team first assessment including date and time

PER Team initial decision outcome, date and time

PER Team review - Change Decision, date and time - and change in observations and Biochemistry PER Team review - Change Decision 2, date and time - and change in observations and Biochemistry

Discharge

Further procedures, length of stay, (including ICU, HDU, Ward), mortality, Place of discharge to. IVC filter insertion.

Follow up

Day 30 (± 7 days): All cause and PE related Mortality, Local readmission – Patient questionnaire: PEmb-QoL, EQ-5D-5L, Borg Scale

Day 90 (± 14 days): Mortality, Local readmission – Patient questionnaire: PEmb-QoL, EQ-5D-5L, Borg Scale

6 months (+/- 30 days): All cause and PE related Mortality – Patient questionnaire: PEmb-QoL, EQ-5D-5L, Borg Scale

Those undergoing CAVT will have the following additional data collected:

Procedural success and outcome. Procedural time, Access route, Aspiration device used, Separator used, Heparin given, including dose, Concurrent Lysis used, including dose. Thrombectomy time. Pulmonary arterial pressure at start, Pulmonary Arterial pressure at finish. Requiring further procedures, Length of stay, IVC filter insertion, readmission along with:

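### Section 3.1 decides who is approached by PESI score, while the eligibility criteria and section 4.2 use the ESC class; the two are not linked, and the rule that forms the risk groups is not named

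*Protocol*

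**What the plan says.** **Who is approached.** Protocol section 3.1 (Screening procedures) divides patients with CT-diagnosed PE into "low, intermediate or high risk as per normal standard of care using the PESI score". It continues: "All patients who are intermediate or high risk and referred to the local Pulmonary Embolism Response Team (PERT) and if eligible will be approach" for consent. No PESI cut-offs for three groups are given.

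**Who is eligible.** Inclusion criterion 3 in section 3.2 reads "Defined as intermediate or high-risk PE (as defined within the ESC Guidelines". Exclusion criterion 3 in section 3.3 reads "Low risk PE as defined by ESC guidelines". The study summary and the flow chart also refer to ESC. Section 4.2 (Recruitment) states: "All patients referred with an intermediate or high-risk PE (according to ESC guidelines (1)) will be included (after consent) into the wider dataset".

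**What is recorded.** The baseline items in section 7.2 begin "PESI score, , RV/LV ratio CT, RV/LV ratio USS". Appendix 1 has a row for the PESI score. Neither place has an item for ESC class.

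**How risk class is used.** Section 6.1 expects roughly a quarter of the thrombectomy group to be high risk and describes that group with the words "As a key comparison of interest of the high-risk subgroup". Section 6.2 summarises the primary outcome by risk group as well as overall. Neither section says which scheme defines the groups.

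**The concern.** Risk class does three jobs in this study: it controls entry, it organises the primary results, and it describes the case mix on which hospitals are compared. If the step that decides who is approached uses one scheme and the eligibility criteria use another, the cohort depends on which section a site follows. Secondary objectives 5 and 6 concern the effect of service design on CAVT rate and outcomes, and variation in CAVT provision between hospitals. A difference in screening rule would change both the denominator of the CAVT rate and the severity mix at a site, for a reason unrelated to service design or practice. Objectives 4 and 7, on high-risk patients and on severity, need a risk class with one known meaning.

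**Working it through.** This is a comparison of texts; the only arithmetic is the planned size of the subgroup.

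**Step 1. Are the schemes linked?** Section 3.1 uses PESI. The summary, flow chart, 3.2, 3.3 and 4.2 use ESC. The protocol neither reproduces the ESC definition nor says how PESI groups correspond to ESC classes. They must be treated as two rules.

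**Step 2. What happens to each type of patient?** Take patients who are referred to PERT and meet every other criterion. Read 3.1 in its most favourable form, as a PESI screen followed by a check of the formal criteria.

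| PESI | ESC | Section 3.1, then 3.2 and 3.3 | Section 4.2 |
|---|---|---|---|
| low | low | not approached | not included |
| low | intermediate or high | not approached | included |
| intermediate or high | low | removed by exclusion 3 | not included |
| intermediate or high | intermediate or high | approached, eligible | included |

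The sections agree in three rows and conflict in the second. An eligibility check made after the PESI screen can only remove patients; it cannot bring back someone the screen has passed over.

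**Step 3. What differs between sites?** A site following 3.1 enrols only the fourth row. A site following 3.2 and 4.2 enrols the second and fourth. The first cohort is a subset of the second, so any difference runs in one direction: the site following 3.1 loses patients who are low by PESI.

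**Step 4. Can the class be rebuilt from the data?** Perhaps. Section 7.2 also lists blood pressure, pulse, saturations, GCS, BNP, troponin, CT right heart strain findings, RV/LV ratio on CT and ultrasound, and thrombolysis. Two features weaken a later derivation. Observations and biochemistry are listed under admission or diagnosis, whereas PESI is listed under the day of PERT referral when that differs. Troponin is in section 7.2 but not in the biochemistry rows of Appendix 1. A derived class also need not match the one the site applied at entry.

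**Step 5. What rests on the class?** Planned participants: 2,000, all classified. Planned high-risk CAVT patients: 25% × 200 = 50. The 25% is not tied to either scheme, so the size of the subgroup also depends on a rule that is not stated.

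**The case against.** The best defence is that ESC governs eligibility wherever criteria are listed, that 3.1 only describes triage, and that its reference to eligible patients points back to 3.2 and 3.3. Much of this stands: it removes the conflict for patients who are intermediate or high by PESI but low by ESC. It does not help the patient who is low by PESI and intermediate or high by ESC.

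A second defence is that defining analysis subgroups commonly belongs in the SAP. That is fair for the risk groups taken alone. But section 6.2 has the SAP finalised only before database lock, and it cannot recover patients who were never approached.

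Four stronger readings are tempting and are not supported.

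- A reader might infer that PESI is the only risk information recorded. Section 7.2 presents its list as a sample and includes haemodynamic, biomarker and right-heart data. PESI is only the sole named classification.
- A reader might infer that the high-risk subgroup is built on two rules. Sections 6.1 and 6.2 name none; the rule is unstated.
- A reader might take section 4.2, which does not repeat the cardiac dysfunction requirement of inclusion 7, as a third entry rule. It is a summary that also omits age, symptom duration and the exclusions.
- A reader might want a count of misclassified patients. Any assumed discordance rate would have no anchor in the protocol. It would also merge the low/intermediate boundary, which affects who is approached, with the intermediate/high boundary, which affects the subgroup of about 50.

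**Conclusion.** The point holds as an internal inconsistency. Section 3.1 cannot be followed together with section 4.2 for a patient who is low by PESI but intermediate or high by ESC, and the protocol does not say which scheme forms its risk groups. The practical effect assumes that some such patients exist and that at least some sites apply 3.1 as written. The protocol does not show how often the schemes disagree, or whether one draws on the other, so the number of patients affected cannot be given. What can be given is the reach: the approach step for the whole cohort of 2,000, the comparability of 12 sites, and a planned subgroup of about 50. This warrants correction because lost approaches cannot be repaired at analysis. It does not show that the cohort is biased or that the risk groups cannot be formed.

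**What to change.** 1. Reconcile section 3.1 with sections 3.2, 3.3 and 4.2 so that one named classification decides both who is approached and who is eligible. The choice of scheme is for the sponsor and the clinical team. The criteria lists and section 4.2 already name ESC, so keeping it would need the fewest edits.
2. Record that class, as assessed at PERT referral, as a baseline item in section 7.2 and a row in Appendix 1.
3. State in sections 6.1 and 6.2 that the same class defines the risk groups and the high-risk subgroup, and that the 25% planning share refers to it.
4. Keep PESI as a separate severity covariate for the regression analyses.

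The cost is a rewording of section 3.1, short additions to 6.1 and 6.2, one database field and one schedule row. Treatment, visits and target numbers do not change. The edit should be made before screening begins or, if it has begun, by early amendment, with each site asked which rule it has been applying.
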